Study Protocol

Effects of a Compliant Arm Support on Post-stroke Upper Extremity Range of Motion

Principal investigator:	[name] [name] of Mechanical Engineering Stanford University Stanford, CA, USA
ClinicalTrials.gov identification number	NCT03867838
Protocol identification number	IRB-49194
Author	[name] Redwood City, CA, USA
Version	Draft 0.3
Date	8 January, 2021

Signature page

Principal investigator:

[name]

Author

[name]

Table of contents

I. Introduction	4
II. Aims and objectives	4
III. Study design	4
III.a. Participant recruitment	4
III.b. Study protocol	5
IV. Analyses	6
IV.a. Reachable workspace area computation	6
IV.b. Estimate of flexor synergy activation (biceps electromyography)	6

I. Introduction

The aim of this study is to test in a single-center self-controlled study whether a custom lightweight, low-cost compliant exoskeletal arm support assists stroke survivors to achieve a greater reachable workspace area with the impaired arm and whether any such effect might persist when the device is no longer in use.

This protocol and statistical analysis plan will give more detailed descriptions of the methodology, analyses, and endpoints of this study.

II. Aims and objectives

The aim of this study is to test the efficacy of an experimental compliant arm support designed to support shoulder abduction in human users. We consider two ways in which such a device might be helpful for stroke survivors: (1) improved functionality while using the device and (2) residual benefits that persist after use of the device. In Section III, we describe the protocol we developed to examine whether our device increases the reachable workspace area and whether any improvements persist for a short period of time after an intervention.

III. Study design

The study is a single-arm pilot study designed to assess whether an experimental compliant arm support (1) assists stroke survivors to achieve a larger reachable workspace area and (2) whether a short assisted exercise trial causes a residual increase in reachable workspace area caused by a reduction in flexor synergy activation.

III.a. Participant recruitment

Candidate participants will be identified in one of the following manners:

(1) referral from treating physician through the Stanford Neurology & Neurological Sciences and Physical Medicine & Rehab clinics (both outpatient). Patients with clinic appointments and history of stroke will be screened under a waiver of authorization for recruitment, guided by inclusion/exclusion criteria. The physician will discuss the study with the patient and if the patient agrees, a physician or coordinator from the study team will approach the patient after the patient's clinic appointment.

(2) through a database in which stroke survivors from the community have indicated their interest in participating in Stanford stroke research studies and filled out a form to add themselves to a database. Study personnel may contact individuals directly from that list.

(3) from a list of subjects who enrolled in other stroke research studies at Stanford and indicated that they are interested in participating in more stroke studies. These are current patients of the study physicians. Study personnel may contact these individuals directly.

Once identified, candidate participants will be contacted via phone call and asked to answer a few questions to establish eligibility and interest. Participants will be scheduled only if they express interest and meet the inclusion criteria determined during the phone screening.

To be included in the study, all participants must:

- be at least 18 years of age
- be greater than 6 months post stroke
- exhibit passive abduction to 90 degrees at shoulder
- exhibit reduced active (retro)flexion/extension at shoulder when abducted to 90 degrees
- exhibit reduced active flexion/extension at the elbow

Participants will be excluded from all assessments if they:

- are unable to give informed consent
- are unable to comprehend and follow instructions
- have a condition (other than stroke) affecting sensorimotor function
- show evidence of unilateral spatial neglect
- are unable to sit in a chair (without armrests) for at least 2 hours (transfer from wheelchair acceptable)

We do not have pilot data to power our study. However, previously published studies using similar methods have typically examined 6-12 participants. We aim to enroll up to 10 participants.

III.b. Study protocol

When a participant arrives for the study session, time will first be allocated to review the consent document and answer any questions. Once participants have granted their informed consent, non-invasive clinical assessments will be administered by the study personnel for demographics purposes. These assessments include: the Upper Extremity portion of the Fugl-Meyer Assessment (FMA) and simple tests for joint range of motion, visual/tactile neglect, and scapula-humeral rhythm.

Our protocol consists of a set of assessments performed with each of 2 support conditions: (1) unassisted and (2) using our experimental device. In each assessment, we will measure the reachable workspace area and a proxy for flexor synergy activation. To assess reachable workspace area, participants will be coached to individually flex and extend the elbow and shoulder to trace the largest possible circle while keeping the hand and elbow raised to the height of the shoulder while arm kinematics are measured using an optical motion capture system (Phasespace Impulse X2E, San Leandro, CA, USA). Participants will trace 6 circles per measurement, 3 in each direction (clockwise or counterclockwise) with the order randomly determined. As a proxy measurement for flexor synergy activation, the arm will be placed in a configuration known to activate the flexor synergy — arm raised to shoulder height with the elbow bent 90° with the hand placed directly in front of the sternum — while the activation of the biceps muscle is recorded using electromyography (Delsys Bagnoli 2 system, Natick, MA,

USA). Each participant will complete the first set of assessments unassisted to establish baseline measurements. Participants will then complete a trial while wearing our experimental device. A trial consists of a workspace and flexor synergy evaluation with the assigned support followed by a ten-minute intervention trial. In this intervention trial, participants will perform the same clockwise and counterclockwise circular movements with the hand used to measure the reachable workspace. The direction of the circular movements will be randomly determined and repeated for 1 minute. Up to three 1-minute rest periods will be allowed as needed. The support will then be removed and participants will perform another workspace and flexor synergy assessment with no support to test for any effects of the exercise. Participants will then rest for 30 minutes before performing another workspace and synergy assessment to determine whether any exercise effects have worn off.

IV. Analyses

The subsections below will describe data processing and analyses performed to compute the primary outcome measures.

IV.a. Reachable workspace area computation

Motion capture data is low-pass filtered at 20 Hz using an 8th order, zero-phase shift Butterworth filter. Any gaps in the marker trajectories caused by temporary occlusions (less than 0.2 seconds) of the marker are filled using cubic interpolation. Any occlusions lasting longer than 0.2 seconds are ignored in our analyses rather than interpolated to avoid generating incorrect data. We compute the reachable workspace area of the hand using the boundary function in Matlab, which computes a concave boundary around the input data and returns the area of that boundary. We disregard datapoints in which the hand (defined as the marker on the ulnar epicondyle) or elbow (defined as the marker on the lateral humeral epicondyle) fall below 20 cm below the height of the shoulder (defined as the marker on the acromion).

IV.b. Estimate of flexor synergy activation (biceps electromyography)

Recorded electromyograms (EMG) are high-pass filtered with a cutoff frequency of 30Hz, rectified, and then low-pass filtered with a cutoff frequency of 6Hz to create linear envelopes. All filters are 8th order, zero-phase shift Butterworth filters. We use the average of this linear envelope as the estimate for flexor synergy for a given trial.

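### Aim 2 asks a causal and mechanistic question that one device-assisted bout, with no unassisted-exercise comparator, cannot answer

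*Protocol*

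**What the plan says.** Section III describes a single-arm pilot whose second aim is to learn whether "a short assisted exercise trial causes a residual increase in reachable workspace area caused by a reduction in flexor synergy activation". That sentence holds two causal links: exercise to area, and synergy to area. Sections I and II tie the lasting effect to the device. Section I asks "whether any such effect might persist when the device is no longer in use". Section II, under an aim of testing the device's efficacy, lists "residual benefits that persist after use of the device" as one of two ways in which it might help.

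Section III.b gives one sequence for all:

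- "Each participant will complete the first set of assessments unassisted to establish baseline measurements".
- An assessment in the device follows, and then a ten-minute bout, still in the device, in which "participants will perform the same clockwise and counterclockwise circular movements with the hand used to measure the reachable workspace".
- The device comes off, after which "participants will perform another workspace and flexor synergy assessment with no support to test for any effects of the exercise".
- The last step is a delayed retest, again unassisted: "Participants will then rest for 30 minutes before performing another workspace and synergy assessment to determine whether any exercise effects have worn off".

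Only the direction of the circles is randomised. No exercise bout without the device is described; the unassisted condition applies to assessments. The mechanism measure is biceps EMG: "As a proxy measurement for flexor synergy activation, the arm will be placed in a configuration known to activate the flexor synergy". Section III.a aims for up to 10 participants and says there are no pilot data for a power calculation.

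**The concern.** If the unassisted area is larger after the bout, the present wording invites the conclusion that the device left a residual benefit by damping the flexor synergy. The same increase could follow from practising the circles without the device. This is not a matter to leave to the SAP: no analysis can supply a comparator that the design lacks, and the aim itself is fixed in the protocol.

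**Working it through.** The protocol states no figure to reproduce on this point. The question is what the four assessments can identify.

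**1. Assessments (Section III.b).** A1: baseline, unassisted. A2: in the device. A3: directly after the bout, unassisted. A4: after 30 minutes' rest, unassisted.

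**2. Exposure before A3.** Each measurement takes 6 circles, so A1 and A2 give 6 + 6 = 12 assessment circles. The ten-minute bout of the same movement comes on top.

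**3. What the contrast estimates.** Let *a* be the part of the change due to assistance, *e* the part due to exercising and practising the task in the bout with or without assistance, and *r* the part due to repeat testing and time. Then

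A3 − A1 = *a* + *e* + *r*.

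- Effect of the device: the target is *a*, and *e* + *r* is error.
- Effect of the assisted bout as a package: the target is *a* + *e*, and only *r* is error.

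**4. Rank check.** Take four parameters: mean, device-on effect (A2), assisted-exercise effect (A3), and an effect of repeating the task (A3). The last two share one column, so the design matrix has rank 3 for 4 parameters. With a free effect at A4 it has rank 4 for 5. The matrix reaches rank 4 of 4 if drift is strictly linear over the assessments and the residual effect at A4 is exactly zero. The design cannot test either assumption, and even then only the bout is separated from drift, not assistance from exercise. With a matched unassisted bout in randomised or counterbalanced order, the model with mean, repetition and assistance has full rank (3 of 3).

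**5. The 30-minute retest.** A4 shows whether the change fades. A change that fades fits a passing device effect, but also warm-up or short-lived practice. A change that stays fits a lasting device effect, but also learning.

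**6. Mechanism.** EMG is recorded in a held posture and area during the circles. EMG is observed and not manipulated, so changes in both show association at most. With 10 participants even the association is imprecise. For an assumed correlation of 0.5 between the two changes, Fisher's z is 0.549 ± 1.96/√7 = 0.549 ± 0.741, which gives a 95% CI of −0.19 to 0.86.

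**7. Illustration of size.** Assumptions, none from the protocol: paired t-test, two-sided 5%, and a change due wholly to practice of *d* SDs of the paired difference. With n = 10 there are 9 degrees of freedom, the critical value is 2.262 and the noncentrality is *d*√10.

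| Practice gain *d* | *d*√10 | Chance of a significant increase |
|---|---|---|
| 0 | 0 | 2.5% |
| 0.1 | 0.32 | 4.7% |
| 0.3 | 0.95 | 13.4% |
| 0.5 | 1.58 | 29.3% |
| 0.8 | 2.53 | 61.6% |

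If practice also lowered EMG by 0.5 SD, with independent errors and no link between the two, both changes would be significant in 0.293² = 8.6% of studies, against 0.025² = 0.06% by chance alone.

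**The case against.** The strongest reply is that Section III names the assisted bout, not assistance, as the exposure, and that Section III.b likewise speaks of effects of the exercise. Under that reading, practice within the bout belongs to the effect, and only repeat testing and time threaten the contrast. This stands for the words of Section III alone, and it limits the point. It does not remove it: Sections I and II tie persistence to the device, and the clause about reduced synergy is unsupported under either reading.

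A reader might infer that the fixed order is itself a fault. The documents do not support that. A before-and-after question needs the baseline first, and starting with the device could carry over into the unassisted measurement. Returning to the unassisted state twice gives some within-person control.

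A reader might also take the fixed EMG posture for a weakness in measurement. It keeps readings comparable across assessments, and the protocol openly calls it a proxy. The limit is on inferring mediation, not on the measure.

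Finally, this is a declared single-arm pilot and the aim is worded as a question, so no causal claim has yet been made. That is fair, and it is why rewording is enough.

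**Conclusion.** The point holds: Aim 2 is wrong as written, because neither of its causal links can be established by the design in Section III.b. This rests on the sequence, the single assisted bout and the shared task, all stated in the protocol, and on no assumed number. The percentages show only how a practice gain could be misread as a device effect. They depend wholly on the assumed gain and test, and are not error rates of this trial. They count as errors only when the change is credited to the device.

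Two stronger readings should be resisted. One is that Aim 1 fails too. Device against baseline shares the fixed order but does not lack its comparator, and the documents give neither size nor direction for any change from first to second attempt. The other is that a single-arm study is unacceptable here. It is adequate for describing change; the mismatch lies in the question put to it.

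**What to change.** 1. Section III, Aim 2: replace the text with *change in unassisted reachable workspace area from baseline to after assisted exercise (immediately and after 30 minutes), and whether it is accompanied by a change in biceps EMG*. Drop *causes* and *caused by*.
2. Section II: replace the phrase on residual benefits with *change that remains after use of the device*. Section I is hedged and can stand once item 3 is added.
3. Add one sentence: *Without an unassisted-exercise comparator, residual change is not attributed to the device or to reduced flexor synergy.*

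This changes no procedure and no data. The downside is a more modest conclusion for Aim 2.

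Keeping the device question would instead need a matched unassisted bout in random or counterbalanced order. If it copied the device trial, that would add at least 10 + 30 = 40 minutes plus assessments, for participants whom Section III.a screens only on sitting for 2 hours.

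Two further changes are optional and do not bear on this point: reporting device-on area against the two later unassisted areas as descriptive contrasts for Aim 1, and replacing the reference to an assigned support in Section III.b, since nothing is assigned.

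### Does settling eligibility by telephone let people into the study who fail criteria that only an examination can check?

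*Protocol*

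**What the plan says.** Section III.a of the Protocol describes three recruitment routes: clinic referral, a community database in which stroke survivors register themselves, and a list of people from other stroke studies at the same institution. Candidates on the clinic route are "screened under a waiver of authorization for recruitment, guided by inclusion/exclusion criteria". Once identified, candidates are telephoned and "asked to answer a few questions to establish eligibility and interest". The next sentence sets the condition for a visit: "Participants will be scheduled only if they express interest and meet the inclusion criteria determined during the phone screening".

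The five inclusion criteria include "exhibit passive abduction to 90 degrees at shoulder", reduced active shoulder movement in that position, and reduced active elbow movement. The exclusion list opens with "Participants will be excluded from all assessments if they", and one of its five items is that they "show evidence of unilateral spatial neglect".

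Section III.b then describes the visit. After consent, "non-invasive clinical assessments will be administered by the study personnel for demographics purposes". These comprise the upper-extremity Fugl-Meyer Assessment and "simple tests for joint range of motion, visual/tactile neglect, and scapula-humeral rhythm". The unassisted baseline measurement of workspace and biceps activity follows. Section III.a sets a ceiling of 10 participants and gives no power calculation.

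**The concern.** Read literally, eligibility is decided on the telephone, yet some criteria cannot be decided there. Passive range of motion is found by someone else moving the limb, and neglect is found by testing. The tests that could settle these points are scheduled at the visit, but the purpose given for them is descriptive. No sentence links them to eligibility or says what happens when a person who has consented turns out not to qualify.

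If staff took the descriptive label at face value, they might keep someone who does not meet the criteria. If they applied the criteria, they might use up one of at most 10 places. In so small a study each person is at least 10% of the sample. The shoulder criterion also bears on the measurement itself, because section IV.a discards data recorded with the hand or elbow more than 20 cm below shoulder height. Different handling could therefore seem to produce different analysed samples.

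**Working it through.** **Step 1. Count the criteria that call for an examination.** Inclusion: age and time since stroke can be asked about; the three movement criteria are better examined (3 of 5). Exclusion: neglect needs a test (1 of 5). In total 3 + 1 = 4 of 10. The sentence on scheduling names inclusion criteria only, so it covers three of these four. Neglect is covered by the sentence before it, which speaks of eligibility in general.

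**Step 2. Match them to the visit.** The joint range-of-motion tests in section III.b serve the three movement criteria, and the neglect tests serve the fourth. Each of the four therefore has a corresponding on-site test.

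**Step 3. Check the order of events.** The sequence is telephone call, scheduling, consent, clinical tests, then the unassisted baseline. The tests precede every outcome measurement, so a failure is known before any outcome data exist.

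**Step 4. Check which text governs.** The scheduling sentence is a condition for booking a visit. The inclusion list is separately stated as a requirement on everyone in the study, and the exclusion list bars a person from every assessment. A descriptive label on the tests does not cancel either requirement, and nothing forbids using the results to apply the criteria.

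**Step 5. Size the remaining cost.** The Protocol gives no rate of failure at the visit, so 0 to 2 failures among 10 consented people is an assumption. If failures count toward the ceiling, the half-width of a 95% interval for a mean within-person difference, in units of the standard deviation of that difference, is t(0.975, n − 1)/√n:

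| n | t | √n | Half-width (SD) | Ratio to n = 10 |
|---|---|---|---|---|
| 10 | 2.2622 | 3.1623 | 0.715 | 1.00 |
| 9 | 2.3060 | 3.0000 | 0.769 | 0.769/0.715 = 1.07 |
| 8 | 2.3646 | 2.8284 | 0.836 | 0.836/0.715 = 1.17 |

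If failures do not count, they can be replaced and the loss is zero. The table prices the correct exclusion of people who do not qualify; it does not measure any effect of the telephone wording or of the label on the tests. There is no planned precision or power to compare it with. A sample of 8 or 9 respects the ceiling and lies within the 6 to 12 participants that the Protocol cites from similar studies.

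**The case for a change.** The strongest case for a change is that where eligibility is decided, and what the screening tests are for, belongs in a protocol rather than an analysis plan. This Protocol addresses both points, and the two statements do not fit its own criteria. Treating the call as a condition for scheduling only does not close the gap, because the later check is then nowhere named. The bar on all assessments heads the exclusion list alone, so it does not reach the three movement criteria. The community-database route has no stated examination before the visit. A remedy would take about two sentences and add no procedure.

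Much of this stands as a comment on wording. The mismatch is real, and the community route is the one most exposed: clinic patients are screened against the criteria, and people on the third route are already under the study physicians' care. The point about the heading is also right, but the movement criteria have their own binding statement, since the inclusion list is imposed on every participant.

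What does not stand is the step from loose wording to different samples. A team that kept someone who failed a test would be departing from the stated criteria, not choosing between two permitted readings. The study has a single center, so practice cannot diverge between sites. The two reduced-movement criteria carry no numerical threshold, so telephone questions are a workable first filter for them. How to count a consented person who then fails is a bookkeeping matter that can be settled outside the Protocol.

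**Conclusion.** No change to the plan is called for. The Protocol describes the telephone call too strongly and the on-site tests too narrowly, but its criteria are binding, the necessary tests are scheduled, and they come before any outcome is measured. Followed as written, it excludes the people it means to exclude. This is a gap in wording that competent staff will fill sensibly.

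No bias in the estimated effect follows. The largest cost that can be put in figures is an interval 7% wider with one lost place or 17% wider with two. That rests on two assumptions: that such failures occur, and that they count toward the ceiling. If either is false, the cost is nil. Rewording would alter no procedure, criterion or analysis. The conclusion assumes that staff apply the listed criteria to what the tests show, as the Protocol requires of them.

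### Does leaving the biceps EMG value in raw amplitude units, without scaling to the participant's own baseline, spoil the flexor synergy comparison?

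*Protocol*

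**What the plan says.** Section IV.b gives the EMG processing: high-pass filter at 30 Hz, rectify, low-pass filter at 6 Hz, average. It ends: "We use the average of this linear envelope as the estimate for flexor synergy for a given trial". No scaling step follows.

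Section III.b says "In each assessment, we will measure the reachable workspace area and a proxy for flexor synergy activation", and "Each participant will complete the first set of assessments unassisted to establish baseline measurements". A baseline EMG value therefore exists for every participant. Later assessments take place with the device on, after the exercise with the device off, and again after 30 minutes of rest. The Introduction calls the study self-controlled.

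The EMG value bears on the second question in section III: "whether a short assisted exercise trial causes a residual increase in reachable workspace area caused by a reduction in flexor synergy activation".

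On scope, the Introduction says "This protocol and statistical analysis plan will give more detailed descriptions of the methodology, analyses, and endpoints of this study", and section IV opens with "The subsections below will describe data processing and analyses performed to compute the primary outcome measures". Section III.a states "We do not have pilot data to power our study" and "We aim to enroll up to 10 participants". No alpha, power, effect size, standard deviation, group summary or test appears for either outcome.

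**The concern.** Surface EMG amplitude can differ between people for reasons unrelated to the flexor synergy. Every step in IV.b passes such a gain straight through to the final number. If raw changes were then averaged over at most ten people, those with large signals would dominate the mean, which could not be read as a typical percent reduction. The EMG value is the only measure of the mechanism in the second question, and a document that calls itself protocol and statistical analysis plan might be expected to fix the scale. The remedy looks cheap, because the baseline is already recorded: compare assessments as a log ratio to it. At stake would be the interpretation of the mean EMG change and, with some tests, power. The workspace result would not be touched.

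**Working it through.** There is no stated figure to reproduce, since the protocol gives no power, variance or effect size. The check has four steps.

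**1. What a gain does.** Let a participant's true envelope means be B (baseline) and F (follow-up), recorded with gain g. IV.b returns gB and gF.

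- Raw change: gF − gB = g(F − B), so it scales with g.
- Ratio: gF / gB = F / B, free of g.

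Running the IV.b steps on a synthetic signal (1000 Hz sampling and 10 s assumed) with gains 0.5, 1, 2 and 4 multiplied the baseline value and the raw change by exactly those factors and left the ratio at 0.749. This part of the concern is correct. It holds only if g is constant within the session, and the sign of each person's change is the same on either scale.

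**2. What raw averaging would do.** Suppose everyone has the same percent change and amplitude a is lognormal between people. A participant's share of the mean raw change is w_i = a_i / Σa_j, and the effective number is 1 / Σw_i². For n = 10 (medians):

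| Assumed between-person log-SD | 0.4 | 0.6 | 0.8 | 1.0 |
|---|---|---|---|---|
| Share of top two (20% if equal) | 31% | 37% | 43% | 49% |
| Effective number of 10 | 8.8 | 7.8 | 6.7 | 5.7 |
| Samples in which top two carry at least half | 0% | 4% | 23% | 47% |

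The arithmetic is right given its assumptions, and the result depends heavily on the assumed spread. If the effect is instead an equal absolute fall D in everyone, each share is D / (10D) = 10%, the top two carry 20%, and the argument disappears.

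**3. What the protocol must say for the harm to occur.**

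| Needed | In the protocol |
|---|---|
| A mean of raw EMG changes over participants | Not stated |
| Effects roughly proportional to amplitude | Not stated |
| A wide spread of amplitude between people | Not stated |

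IV.b stops at one value per assessment. IV.a also stops at one value, an area, with no contrast or test. Section IV covers how the measures are computed. How they are compared is left unwritten for both. The envelope mean is the input that a difference, a ratio or a log ratio would each need, and IV.b rules out none of them.

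**4. Whether the log ratio would be better.** Assumed model: B = a·exp(e₀) + u₀ and F = 0.75·a·exp(e₁) + u₁, with median amplitude 1, n = 10, two-sided 5%, values floored at 0.02 and 20,000 trials per cell. The proportional errors e have log-SD 0.25 and the constant errors u have the SD shown; in the last case only u is present. As a check on the model with proportional error alone: ln 0.75 = −0.288, the SD of the log ratio is 0.25 × √2 = 0.354, and the noncentrality is 0.288 / 0.354 × √10 = 2.57 on 9 df, consistent with the simulated power of about 63% for the log-ratio t-test.

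Comparing like with like, power of the exact signed-rank test at log-SD 0.4/0.6/0.8/1.0:

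| Error | Raw difference | Log ratio | Log ratio minus raw, points |
|---|---|---|---|
| Proportional only | 58/56/55/52% | 61% throughout | +3/+5/+6/+9 |
| Proportional plus constant, SD 0.10 | 50/49/46/44% | 51/48/45/41% | +1/−1/−1/−3 |
| Proportional plus constant, SD 0.15 | 43/43/40/39% | 42/39/36/34% | −1/−4/−4/−5 |
| Constant only, SD 0.20 | 69/69/70/69% | 60/54/49/43% | −9/−15/−21/−26 |

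Repeat runs move single entries by one or two points. The log ratio is clearly ahead in one error model of four, level or slightly behind in two, and well behind in one.

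**The case for a change.** The strongest reply is that this is not simply left to a later plan. The document calls itself protocol and statistical analysis plan, section IV speaks of analyses as well as processing, and IV.b goes into filter order and cutoffs before declaring its unscaled result to be the estimate. Scaling would be the natural next step. With ten people and no pilot data, fixing the scale beforehand would also remove a choice made after seeing the results. And one comparison does favor the log ratio plainly: under purely proportional error a t-test on raw change has 55/48/40/31% power, against about 63% on the log ratio.

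Part of this stands. The scale is unwritten, and writing it down would be good practice. But section IV ties its scope to computing the outcome measures, and it treats both alike; the missing comparison is general and not a defect of the EMG value. A relation to own baseline is not absent either: the study is self-controlled, the first assessment is there to set a baseline, and later ones test for exercise effects. Only the scale is open. The power loss quoted for the t-test belongs to a test the protocol does not name and an error structure it does not give, and it largely shrinks with a signed-rank test on the same raw differences (58/56/55/52%).

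**Conclusion.** The concern does not hold. IV.b states nothing wrong, contradicts no other passage and fixes no raw pooling. It defines a usable per-assessment value and leaves the comparison scale open, as the protocol does for workspace area.

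The weighting effect (31% to 49% for the top two instead of 20%) is real only if raw changes are averaged, effects are proportional and amplitudes spread widely. All three are assumptions from outside the document. Even then validity is intact: with no true change and proportional error, the raw t-test rejects in 4.4/3.6/3.1/2.6% of trials and the raw signed-rank test in about 5%, no individual's direction of change is altered, and the workspace answer does not depend on EMG scaling.

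Making the log ratio primary would trade 3 to 9 points of signed-rank power gained under proportional error against 9 to 26 points lost under constant error, with little between the scales in the mixed cases. That is a preference between scales, and the protocol holds no data to settle it. A separate analysis plan, which may exist but is not at hand, is the ordinary place for the choice.
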